#### 12.5.3 The response of MIBG lesions will be assessed on central review using the Curie scale as outlined below. Central review responses will be used to assess efficacy for study endpoint. See [Section 8.2](#) for details on transferring images to the Imaging Research Center.

[figure not shown]
NOTE: This scoring should also be done by the treating institution for end of course response assessments.

The body is divided into 9 anatomic sectors for osteomedullary lesions, with a 10th general sector allocated for any extra-osseous lesion visible on MIBG scan. In each region, the lesions are scored as follows. The **absolute extension score** is graded as:

0 = no site per segment,

1 = 1 site per segment,  
2 = more than one site per segment,  
3 = massive involvement (>50% of the segment).

The **absolute score** is obtained by adding the score of all the segments. See diagram of sectors below:

The **relative score** is calculated by dividing the absolute score at each time point by the corresponding pre-treatment absolute score. The relative score of each patient is calculated at each response assessment compared to baseline and classified as below:

1. **Complete response:** all areas of uptake on MIBG scan completely resolved. If morphological evidence of tumor cells in bone marrow biopsy or aspiration is present at enrollment, no tumor cells can be detected by routine morphology on two subsequent bilateral bone marrow aspirates and biopsies done at least 21 days apart to be considered a **Complete Response**.
2. **Partial response:** Relative score  $\leq 0.2$  (lesions almost disappeared) to  $\leq 0.5$  (lesions strongly reduced).
3. **Stable disease:** Relative score  $> 0.5$  (lesions weakly but significantly reduced) to 1.0 (lesions not reduced).
4. **Progressive disease:** New lesions on MIBG scan.

#### 12.5.4 Overall Response Assessment

Table 4: Overall Response Evaluation for Neuroblastoma Patients and MIBG Positive Disease Only

If patients are enrolled without disease measurable by CT/MRI, any new or newly identified lesion by CT/MRI that occurs during therapy would be considered progressive disease.

MIBG	CT/MRI	Bone Scan	Bone Marrow	Catechol	Overall
PD	Any	Any	Any	Any	PD
Any	New Lesion	Any	Any	Any	PD
Any	Any	PD	Any	Any	PD
Any	Any	Any	PD	Any	PD
SD	No New Lesion	Non-PD	Non-PD	Any	SD
PR	No New Lesion	Non-PD	Non-PD	Any	PR
CR	No New Lesion	Non-PD	Non-PD	Elevated	PR
CR	No New Lesion	CR	CR	Normal	CR

### 12.5.5 Overall Best Response Assessment

Each patient will be classified according to his “best response” for the purposes of analysis of treatment effect. Best response is determined from the sequence of the overall response assessments as described in [Section 12.9](#).

## 12.6 **Response Criteria for Neuroblastoma Patients with Bone Marrow Involvement**

### 12.6.1 Bone Marrow Involvement

**Note:** patients with bone marrow as the ONLY site of disease are not eligible for this study. Response criteria in this section are intended to be used when assessing marrow involvement as a component of overall response.

Histologic analysis at the local institution of marrow tumor cell involvement is **required** for patients with a history of marrow involvement. Marrow aspirate and biopsy should be evaluated at baseline and every 2 cycles thereafter. Note: If progressive disease is documented by RECIST criteria using tumor measurements or by MIBG scan, then a repeat BM is not needed to confirm PD.

Complete Response: No tumor cells detectable by routine morphology on 2 consecutive bilateral bone marrow aspirates and biopsies performed at least 21 days apart. Normalization of urinary catecholamines or other tumor markers if elevated at study enrollment.

Progressive Disease: In patients who enroll with neuroblastoma in bone marrow by morphology have progressive disease if there is a doubling in the amount of tumor in the marrow AND a minimum of 25% tumor in bone marrow by morphology. (For example, a patient entering with 5% tumor in marrow by morphology must increase to  $\geq 25\%$  tumor to have progressive disease; a patient entering with 30% tumor must increase to  $> 60\%$ ).

In patients who enroll without evidence of neuroblastoma in bone marrow will be defined as progressive disease if tumor is detected in 2 consecutive bone marrow biopsies or aspirations done at least 21 days apart.

Stable Disease: Persistence of tumor in bone marrow that does not meet the criteria for either complete response or progressive disease.

#### 12.6.2 Overall Best Response Assessment

Each patient will be classified according to his “best response” for the purposes of analysis of treatment effect. Best response is determined from the sequence of the overall response assessments as described in [Section 12.9](#).

### 12.7 **Response Criteria for Patients with CNS Tumors**

#### 12.7.1 Measurable Disease

Any lesion that is at minimum 10 mm in one dimension on standard MRI or CT, for CNS tumors.

#### 12.7.2 Evaluable Disease

Evaluable disease is defined as at least one lesion, with no lesion that can be accurately measured in at least one dimension. Such lesions may be evaluable by nuclear medicine techniques, immunocytochemistry techniques, tumor markers, CSF cytology, or other reliable measures.

#### 12.7.3 Selection of Target and Non-Target Lesions

For most CNS tumors, only one lesion/mass is present and therefore is considered a “target” for measurement/follow up to assess for tumor progression/response. If multiple measurable lesions are present, up to 5 should be selected as “target” lesions. Target lesions should be selected on the basis of size and suitability for accurate repeated measurements. All other lesions will be followed as non-target lesions. The lower size limit of the target lesion(s) should be at least twice the thickness of the slices showing the tumor to decrease the partial volume effect (e.g., 8 mm lesion for a 4 mm slice).

Any change in size of non-target lesions should be noted, though does not need to be measured.

#### 12.7.4 Response Criteria for Target Lesions

Response criteria are assessed based on the product of the longest diameter and its longest perpendicular diameter. Development of new disease or progression in any established lesions is considered progressive disease, regardless of response in other lesions – e.g., when multiple lesions show opposite responses, the progressive disease takes precedence. Response Criteria for target lesions:

- **Complete Response (CR):** Disappearance of all target lesions. Off all steroids with stable or improving neurologic examination.
- **Partial response (PR):**  $\geq 50\%$  decrease in the sum of the products of the two perpendicular diameters of all target lesions (up to 5), taking as reference the initial baseline measurements; on a stable or decreasing dose of steroids with a stable or improving neurologic examination.

- **Stable Disease (SD):** Neither sufficient decrease in the sum of the products of the two perpendicular diameters of all target lesions to qualify for PR, nor sufficient increase in a single target lesion to qualify for PD; on a stable or decreasing dose of steroids with a stable or improving neurologic examination.
- **Progressive Disease (PD):** 25% or more increase in the sum of the products of the perpendicular diameters of the target lesions, taking as reference the smallest sum of the products observed since the start of treatment, or the appearance of one or more new lesions.

Increasing doses of corticosteroids required to maintain stable neurological status should be strongly considered as a sign of clinical progression unless in the context of recent wane or transient neurologic change due e.g. to radiation effects.

#### 12.7.5 Response Criteria for Non-Target Lesions:

- **Complete Response (CR):** Disappearance of all non-target lesions.
- **Incomplete Response/Stable Disease (IR/SD):** The persistence of one or more non-target lesions.
- **Progressive Disease (PD):** The appearance of one or more new lesions and/or unequivocal progression of existing non-target lesions.

#### 12.7.6 Response criteria for tumor markers (if available):

Tumor markers will be classified simply as being at normal levels or at abnormally high levels.

#### 12.7.7 Overall Response Assessment

The overall response assessment takes into account response in both target and non-target lesions, the appearance of new lesions and normalization of markers (where applicable), according to the criteria described in the table below. The overall response assessment is shown in the last column, and depends on the assessments of target, non-target, marker and new lesions in the preceding columns.

Target Lesions	Non-target Lesions	Markers	New Lesions	Overall Response
CR	CR	Normal	No	CR
CR	IR/SD	Normal	No	PR
CR	CR, IR/SD	Abnormal	No	PR
PR	CR, IR/SD	Any	No	PR
SD	CR, IR/SD	Any	No	SD
PD	Any	Any	Yes or No	PD
Any	PD	Any	Yes or No	PD
Any	Any	Any	Yes	PD

Each patient will be classified according to his "best response" for the purposes of

analysis of treatment effect. Best response is determined as outlined in [Section 12.9](#) from a sequence of overall response assessments.

## 12.8 Response Criteria for Patients with non-Hodgkin Lymphoma/Histiocytosis

Response and progression will be evaluated in this study using the new international criteria proposed by the revised Response Evaluation Criteria in Pediatric non-Hodgkin Lymphoma Criteria, with modification from the Lugano classification.

### 12.8.1 Disease Parameters

12.8.1.1 Measurable disease: A measurable node must have an LDi (longest diameter) greater than 1.5 cm. A measurable extranodal lesion should have an LDi greater than 1.0 cm. All tumor measurements must be recorded in millimeters (or decimal fractions of centimeters).

12.8.1.2 Non-measured disease: All other lesions (including nodal, extranodal, and assessable disease) should be followed as nonmeasured disease (e.g., cutaneous, GI, bone, spleen, liver, kidneys, pleural or pericardial effusions, ascites).

12.8.1.3 Target lesions: For patients staged with CT, up to six of the largest target nodes, nodal masses, or other lymphomatous lesions that are measurable in two diameters (longest diameter [LDi] and shortest diameter) should be identified from different body regions representative of the patient's overall disease burden and include mediastinal and retroperitoneal disease, if involved.

### 12.8.2 Evaluation of Measurable Disease

#### Complete Response (CR)

*Disappearance of all disease.* CT or MRI should be free of residual mass or evidence of new disease. FDG-PET should be negative.

#### Complete Response Unconfirmed (CRu)

Residual mass is negative by FDG-PET; no new lesions by imaging examination; no new and/or progressive disease elsewhere

#### Partial Response (PR)

50% decrease in SPD (the sum of the products of the largest diameter and the perpendicular diameter for a tumor mass) on CT or MRI; FDG-PET may be positive (Deauville score of 4 or 5 with reduced lesional uptake compared with baseline); no new and/or PD; morphologic evidence of disease may be present in BM if present at diagnosis; however, there should be 50% reduction in percentage of lymphoma cells.

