## ABSTRACT

This subprotocol is a component of the NCI-COG Pediatric MATCH trial APEC1621. The APEC1621SC screening protocol details the process used to identify actionable mutations in patient tumor samples which will determine eligibility for this subprotocol. Here we will conduct a phase 2 trial of LOXO-101 (larotrectinib) in children with recurrent or refractory solid tumors (including non-Hodgkin lymphomas, histiocytoses and CNS tumors) harboring *NTRK* gene fusion proteins.

LOXO-101 (larotrectinib) has shown tumor regression in non-clinical cancer models and in patients with tumors harboring *NTRK* gene fusion proteins. This is a Phase 2 study of LOXO-101 (larotrectinib) an orally bioavailable, potent, ATP-competitive, selective inhibitor of TRKA, TRKB, and TRKC in patients enrolled in APEC1621 who are determined to have *NTRK* 1, 2 or 3 translocations. LOXO-101 (larotrectinib) will be given orally or through NG- or G- tube at a dose of 100 mg/m^2/dose BID (capped at 100 mg per dose). The primary endpoint will be objective response rate as determined by RECIST. Progression free survival (PFS) will be assessed as a secondary endpoint. In addition, toxicity will be assessed, the pharmacokinetics of LOXO-101 (larotrectinib) in children will be evaluated and the ability to detect *NTRK* fusions in circulating cell-free tumor DNA in plasma will be evaluated.

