 If patients have Grade 4 neutropenia then CBCs should be checked at least every other day until recovery to Grade 3 or until meeting the criteria for dose limiting toxicity.

 If patients develop Grade 4 thrombocytopenia then CBCs should be checked every 3 to 4 days until recovery, per [Section 6.1](#).

 Tumor Disease Evaluation should be obtained on the next consecutive cycle after initial documentation of either a PR or CR. Subsequent scans may restart 2 cycles after the confirmatory scan. If the institutional investigator determines that the patient has progressed based on clinical or laboratory

evidence, he/she may opt not to confirm this finding radiographically.

- 4-A Neurological exam also required for CNS patients.
- 4-B Non- Hodgkin Lymphoma/ Histiocytosis patients are required to have PET scans within 2 weeks prior to start of therapy and should also be followed with PET scans if positive at diagnosis. Refer to [Section 12.8](#)
- 4-C Patients with neuroblastoma must have both CT/MRI and MIBG scintigraphy prior to enrollment if the patient was enrolled with or has a history of having MIBG avid tumor. Otherwise the patient must have both CT/MRI and bone scan prior to enrollment. For patients with neuroblastoma and measurable disease by CT or MRI, lesions should be measured and followed using the same modality (CT or MRI) in addition to MIBG or bone scan. For patients with neuroblastoma and evaluable disease by MIBG scintigraphy or bone scan, use the same modality (MIBG scintigraphy or bone scan) to image and follow patients; CT/MRI are not required but may be performed as clinically indicated. Refer to [Section 12.5.4](#) and [Section 12.9](#).
- 5 Bone marrow aspirate and/or biopsy only required in patients suspected of having bone marrow metastasis on the basis of history, symptoms, laboratory evaluation or other clinical data. Should only be performed on patients with known bone marrow involvement at baseline.
- 6 Bone marrow aspirate and/or biopsy should be performed only when complete response or partial response is identified in target disease or when progression in bone marrow is suspected.
- 7 Medication diary (see [Appendix III](#)) should be reviewed weekly during cycle 1, after completion of each treatment cycle, and uploaded into RAVE.
- 8 See [Section 8.3](#) for details of PK studies.

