**12.3.3.6Cytology, Histology:** These techniques can be used to differentiate between partial responses (PR) and complete responses (CR) in rare cases (e.g., residual lesions in tumor types, such as germ cell tumors, where known residual benign tumors can remain).

Cytology should be obtained if an effusion appears or worsens during treatment when the measurable tumor has met criteria for response or stable disease.

**12.3.3.7FDG-PET:** While FDG-PET response assessments need additional study, it is sometimes reasonable to incorporate the use of FDG-PET scanning to complement CT scanning in assessment of progression (particularly possible 'new' disease). New lesions on the basis of FDG-PET imaging can be identified according to the following algorithm:

- a. Negative FDG-PET at baseline, with a positive FDG-PET at follow-up is a sign of PD based on a new lesion.
- b. No FDG-PET at baseline and a positive FDG-PET at follow-up: If the positive FDG-PET at follow-up corresponds to a new site of disease confirmed by CT, this is PD. If the positive FDG-PET at follow-up is not confirmed as a new site of disease on CT, additional follow-up CT scans are needed to determine if there is truly progression occurring at that site (if so, the date of PD will be the date of the initial abnormal FDG-PET scan). If the positive FDG-PET at follow-up corresponds to a pre-existing site of disease on CT that is not progressing on the basis of the anatomic images, this is not PD.

**Note:** A 'positive' FDG-PET scan lesion means one that is FDG avid with an uptake greater than twice that of the surrounding tissue on the attenuation corrected image.

For patients with a positive PET scan at diagnosis, PET can be used to follow response in addition to a CT scan using the International Pediatric non-Hodgkin Lymphoma Response Criteria.

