#### Progressive disease

For those with > 25% increase in SPD on CT or MRI, Deauville score 4 or 5 on FDG-PET with increase in lesional uptake from baseline, or development of new morphologic evidence of disease in BM

12.8.3 Evaluation of Non-measured Lesions (CT-based response, PET/CT based response not applicable)

Complete Response (CR): Absent non-measured lesions.

Partial response (PR): Absent/normal, regressed, lesions, but no increase.

Stable Disease (SD): No increase consistent with progression

Progressive Disease (PD): New or clear progression of preexisting non-measured lesions.

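### The lymphoma/histiocytosis partial-response rule excuses residual marrow disease only if it was there at original diagnosis, so a patient whose marrow became involved before study entry can be refused PR; the 50% marrow reduction has no stated reference

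*Combined protocol and SAP*

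**What the plan says.** The Abstract describes the population as "children with recurrent or refractory solid tumors (including non-Hodgkin lymphomas, histiocytoses and CNS tumors"), so patients enter some time after their original diagnosis.

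Section 12.8.2 gives the response rules for non-Hodgkin lymphoma and histiocytosis:

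- **PR, marrow:** "morphologic evidence of disease may be present in BM if present at diagnosis; however, there should be 50% reduction in percentage of lymphoma cells". The first half is conditioned on diagnosis. The second half names no time point from which the reduction is measured.
- **PR, PET:** "FDG-PET may be positive (Deauville score of 4 or 5 with reduced lesional uptake compared with baseline"). The reference here is baseline. The rule also excludes new or progressive disease.
- **PD:** "Deauville score 4 or 5 on FDG-PET with increase in lesional uptake from baseline, or development of new morphologic evidence of disease in BM".
- **CR:** "FDG-PET should be negative", with no condition about diagnosis. CRu likewise needs a PET-negative residual mass.

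The trigger for serial PET is also tied to diagnosis. Footnote 4-B in Section 8.1 requires a PET in the two weeks before treatment for these patients, then says they "should also be followed with PET scans if positive at diagnosis". Section 12.3.3.7 has a permissive version: "For patients with a positive PET scan at diagnosis, PET can be used to follow response in addition to a CT scan".

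Under Section 12.3.1.1, an evaluable patient without a centrally confirmed CR or PR is a non-responder.

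**The concern.** A response rule should compare the patient on study drug with the same patient just before study drug. In relapsed disease the marrow can become involved after diagnosis, and Section 4.1.6.1 makes patients with known marrow metastatic disease eligible if they meet the blood counts. Marrow disease at entry is therefore foreseen, and nothing ensures that it was also there at diagnosis. If the condition is applied as worded, the assessor must refuse PR to a patient whose disease has clearly shrunk, because of a marrow finding that predates the trial by an unknown interval. PR counts toward the primary endpoint, which is decided by three responses in 20 patients.

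The missing reference for the 50% reduction is a separate gap: two assessors with the same data could reach different answers. The PET trigger is a lesser matter. A patient whose PET was negative or not done at diagnosis, but positive before therapy, is not directed to serial PET, although CR and CRu need a negative scan and PD can be called on PET.

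**Working it through.** **1. Which time point each rule uses**

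| Rule | Reference |
|---|---|
| Solid tumour PR (12.4.1) | baseline sum of diameters |
| CNS PR (12.7.4) | initial baseline measurements |
| Neuroblastoma MIBG relative score (12.5.3) | pre-treatment score |
| Neuroblastoma marrow progression (12.6.1) | marrow status at enrolment |
| Which patients have marrow studies (8.1, footnote 5) | known involvement at baseline |
| Lymphoma PR and PD, PET uptake (12.8.2) | baseline |
| Lymphoma PR, residual marrow allowed (12.8.2) | **diagnosis** |
| Lymphoma PR, 50% marrow reduction (12.8.2) | **none stated** |
| Serial PET trigger (8.1 footnote 4-B; 12.3.3.7) | **diagnosis** |

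The marrow clause and the PET trigger stand apart from the rest. No definition equates diagnosis with study entry, and footnote 4-B uses the pre-therapy time point and diagnosis as separate things in one sentence.

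**2. A patient run through the PR rule** (marrow percentages assumed for illustration)

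- Marrow clear at diagnosis, 20% lymphoma cells at entry, 10% on study; 50% fall in the sum of products of diameters (SPD); no new lesions.
- Fall from study baseline: (20 − 10)/20 = 50%, so the size of the marrow fall qualifies.
- Marrow disease remains and was not present at diagnosis, so the clause is not met and PR is refused.
- CR is not available either, because it needs all disease to disappear. Section 12.3.1.1 then makes the patient a non-responder.

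**3. The unstated reference** (assumed values)

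- 60% at diagnosis, 30% at baseline, 30% on study.
- From diagnosis: (60 − 30)/60 = 50%. From baseline: (30 − 30)/30 = 0%.
- For the patient in step 2, diagnosis is 0%, and a percentage reduction from zero is undefined.

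**4. The plan's design figures**

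Inputs from Section 11.3.1: N = 20, success if at least 3 responses, null rate 5%, target rate 25%, alpha 10%, power 90%. Exact binomial:

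- Alpha: P(X ≥ 3 | 20, 0.05) = 0.0755. The stated 10% is the design ceiling.
- Power: P(X ≥ 3 | 20, 0.25) = 1 − (0.75^20 + 20·0.25·0.75^19 + 190·0.25²·0.75^18) = 1 − (0.0032 + 0.0211 + 0.0669) = 0.9087.

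The design reproduces.

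**5. Size if patients are refused**

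The documents give no expected number of affected patients, so the number m is assumed. If m patients can never count as responders, power is P(X ≥ 3 | 20 − m, 0.25):

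| m | Power |
|---|---|
| 0 | 90.9% |
| 1 | 88.9% |
| 2 | 86.5% |
| 3 | 83.6% |

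For m = 1: 1 − (0.75^19 + 19·0.25·0.75^18 + 171·0.25²·0.75^17) = 1 − (0.0042 + 0.0268 + 0.0803) = 0.8887. One true responder refused lowers the observed rate by 1/20 = 5 percentage points. Refusals can only lower the chance of declaring success, so they do not inflate the false-positive rate.

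**The case against.** The strongest reply is that a sensible assessor would take diagnosis to mean study entry. PET uptake in the same rule is compared with baseline, footnote 5 ties marrow studies to involvement at baseline, and the affected group is very small: lymphoma or histiocytosis, marrow clear at diagnosis, involved at entry, and not fully cleared despite a qualifying SPD response. The point about size stands. The point about meaning does not settle the matter, because footnote 4-B keeps the two time points apart and the PR rule itself uses both words.

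Four stronger readings are tempting, and the documents do not support them.

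- *PET response is judged against diagnosis.* It is not. Both PR and PD compare uptake with baseline; only the trigger for serial PET mentions diagnosis. That trigger does not forbid PET in other patients, and PR can still be met on CT or MRI.
- *A patient with marrow disease at diagnosis, clear at entry and positive again on study could be PR.* The PR rule excludes new or progressive disease, PD includes "development of new morphologic evidence of disease in BM", and Section 12.2 gives progression precedence.
- *The wording also grants PR wrongly, because the 50% is measured from diagnosis.* The text gives no reference; diagnosis would have to be supplied by the reader. A wrong grant would still need the 50% SPD fall and central confirmation. This is an ambiguity to close and gives no basis for a false-positive estimate.
- *Responder status feeds PFS.* Section 11.7 counts progression, recurrence or death. PR status is not an input. The PET trigger can affect when progression is detected, which is a different route.

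**Conclusion.** The point holds in a narrow form. The marrow condition in the lymphoma/histiocytosis PR rule uses a time point that does not fit a relapsed or refractory population, and followed literally it turns a qualifying responder into a non-responder for the primary endpoint. The 50% marrow reduction lacks a reference. The serial-PET trigger has the same wording problem, with consequences for CR and progression ascertainment and little for ORR.

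The size is small and its frequency unknown. With one patient of 20 assumed always refused, and a true response rate of 25%, power falls from 90.9% to 88.9%. This rests on the literal reading of the clause and on an assumed count that the documents do not supply. N = 20 and the rule of at least 3 responses are unaffected.

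**What to change.** In Section 12.8.2, replace the marrow clause of PR with wording such as: *marrow disease may remain if it was present at study baseline (the pre-study evaluation in the 14 days before protocol therapy), with at least a 50% reduction in the percentage of lymphoma cells compared with that baseline marrow*.

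In Section 8.1 footnote 4-B and Section 12.3.3.7, make the serial-PET condition refer to the mandatory pre-therapy PET in place of the PET at diagnosis.

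The cost is a wording amendment. The pre-therapy PET is already required for these patients, and Section 4.0 already requires marrow, when applicable, in the 14 days before therapy. Some patients who are PET-positive only at study entry would now be directed to serial PET. If patients in this group have already been assessed, central review should confirm which reference was used for their marrow.
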